10.8 Resistance Analyses

For all subjects, full length NS3/4A and NS5A will be sequenced from baseline samples by next generation sequencing (NGS). For all subjects who experience virologic failure (on-treatment virologic failure or Relapse_{overall} as defined in Section 10.1), full length NS3/4A and NS5A genes from the first sample after virologic failure with HCV RNA ≥ 1000 IU/mL will be sequenced by NGS. For all other subjects who do not achieve SVR₁₂ or SVR₂₄ (prematurely discontinued study drug with no on-treatment virologic failure, HCV reinfection, missing SVR₁₂ or SVR₂₄ data or other reasons as described in Section 10.1, **Reasons for SVR₁₂ Non-Response** and **Reasons for SVR₂₄ Non-Response**) but have a post-treatment time point with HCV RNA ≥ 1000 IU/mL, full length NS3/4A and NS5A genes from the first post-treatment sample with HCV RNA ≥ 1000 IU/mL will also be sequenced by NGS.

For all subjects who do not achieve SVR₁₂ or SVR₂₄, a listing by subject that includes HCV genotype/subtype, reason for SVR₁₂ or SVR₂₄ non-response, and baseline resistance data availability besides key baseline characteristics will be produced.

For each DAA target, signature amino acid positions and a key subset of amino acid positions for the respective inhibitor class are shown in [Table 8](#). Appropriate subtype-specific prototypic reference sequences will be used for comparison with sequences from samples.

Table 8. Signature Amino Acid Positions and Key Subsets of Amino Acid Positions

Target/Genotype	Signature Amino Acid Positions	Key Subset of Amino Acid Positions
NS3		
5, 6	36, 43, 54, 55, 56, 80, 155, 156, 168	155, 156, 168
NS5A		
5, 6	24, 28, 29, 30, 31, 32, 58, 92, 93	24, 28, 30, 31, 58, 92, 93

Included time points for analyses on available samples from subjects who do not achieve SVR₁₂ are: 1) the sample closest in time after HCV virologic failure/treatment discontinuation with an HCV RNA level of ≥ 1000 IU/mL, and 2) 24 weeks post-DAA treatment, provided that resistance-associated variants were detected by NGS at the time of HCV virologic failure/ treatment discontinuation.

The following definitions will be used in the resistance analyses:

- Baseline polymorphism: a polymorphism by NGS in a baseline sample ($\geq 2\%$ or $\geq 15\%$ prevalence within a subject's viral population depending on polymorphism frequency threshold utilized) that was not present in the appropriate prototypic reference amino acid sequence for a given DAA target (NS3 or NS5A).
- Variant at signature amino acid position: variant (relative to reference) present in a baseline or a post-baseline sample at a signature amino acid position.

- Post-baseline substitution: an amino acid substitution in a post-baseline time point sample that was not detected at baseline ($< 2\%$) in the subject and is detectable in $\geq 2\%$ of the sequences from the post-baseline sample.
- Enriched variant: a variant present in both the baseline and a post-baseline sample whose prevalence in the post-baseline sample is at least 20 percentage points greater than the prevalence in the baseline sample [(post-baseline % – baseline %) ≥ 20].
- Treatment-emergent substitution by NGS: a post-baseline substitution or an enriched variant.

Analysis 1

The following analyses will be performed for all subjects, separated by HCV genotype/subtype (including total):

- A listing of all subjects with baseline polymorphisms (2% detection threshold) at signature amino acid positions for each DAA target (NS3 and NS5A) in the ITT population. HCV genotype/subtype and treatment outcome (SVR₁₂ or reason for SVR₁₂ non-response) will be displayed for each subject.
- The number and percentage of subjects with baseline polymorphisms at signature amino acid positions at detection thresholds of 2% and 15% for subjects in the ITT population. This table includes prevalence of each baseline polymorphism, and a summary of the number of subjects with polymorphisms in NS3 only, NS5A only, any in NS3 or NS5A, and in both NS3 and NS5A.
- Total number and percentage of subjects in the ITT population with baseline polymorphisms *at a key subset of amino acid positions* in NS3 only, in NS5A only, in NS3 + NS5A, any in NS3, any in NS5A, and any in NS3 or NS5A at 15% detection threshold.

Analysis 2

The impact of baseline polymorphisms on treatment outcome will be assessed for the **mITT-GT-VF** population as follows: for each polymorphism, the SVR₁₂ rate will be calculated for subjects with and without the polymorphism and the two rates will be

compared using Fisher's exact test. Analysis will be grouped by HCV genotype/subtype (including total) and DAA target (NS3 or NS5A). The analysis will include the number of subjects within each genotype/subtype (including total) with polymorphisms in NS3 only, in NS5A only, any in NS3 or NS5A, and in both NS3 + NS5A.

The following will be included in the analyses of impact of baseline polymorphisms on treatment outcome:

- For each signature amino acid position, presence of any polymorphism at that position (vs no polymorphism at that position), using detection thresholds of both 2% and 15%.
- Each individual polymorphism at each signature amino acid position (vs not that polymorphism) using detection thresholds of 2% and 15%.

Analysis 3

In subjects with or without baseline polymorphisms in NS3 only, in NS5A only, in NS3 + NS5A, any in NS3, any in NS5A, and any in NS3 or NS5 ***at the key subset of amino acid positions*** at 15% detection threshold, the SVR₁₂ rate will be calculated for the **mITT-GT-VF** population, and the rates with or without polymorphisms will be compared using Fisher's exact test. Analysis will be separated by HCV genotype/subtype (including total).

Analysis 4

The following listings will be produced for subjects who do not achieve SVR₁₂ or SVR₂₄ and have post-baseline sequence available. HCV genotype/subtype and reason for SVR₁₂ or SVR₂₄ non-response will be displayed for each subject.

- Listings by subject and time point of all *treatment-emergent substitutions* relative to the baseline amino acid sequences will be provided for each DAA target (NS3 and NS5A).
- Listings by subject and time point of all *variants at signature amino acid positions* in a post-baseline time point relative to the appropriate prototypic

reference amino acid sequence will be provided for each DAA target (NS3 and NS5A).

HCV Genotype/Subtype

Phylogenetic analysis will be conducted on HCV sequence from baseline samples for all subjects in order to accurately determine their genotype/subtype.

Subjects' HCV genotype and subtype may be assessed based on the Inno-LiPA 2.0 Assay used by the Central lab (Covance), the HCV genotype determination by Sanger sequencing a region of NS5B by the Central lab (Covance) and/or from phylogenetic analysis of the full length NS3/4A, and/or NS5A sequences performed by AbbVie. If the phylogenetic analysis is available, then it will be used to determine the subject's HCV genotype and subtype. If it is not available, then the Sanger sequencing assay result will be used to determine the subject's HCV genotype and subtype, if available. Finally, if neither the phylogenetic analysis results nor the Sanger sequencing assay results are available, then the Inno-LiPA assay results will be used to categorize the subject.

This subtype information will be presented in summaries of efficacy subgroup analyses. The baseline characteristic summary will use the results from the central laboratory (Sanger sequencing or Inno-LiPA 2.0 Assay [if Sanger sequencing not available]).

A summary of HCV subtype as provided by the central laboratory (Sanger sequencing or Inno-LiPA 2.0 Assay [if Sanger sequencing not available]) versus phylogenetic analysis also will be provided.

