5.3.3.3 HCV Resistance Variables

For all subjects receiving study drug, the variants at signature resistance-associated amino acid positions at baseline identified by next generation sequencing (NGS) will be compared to the appropriate prototypic reference sequence.

The following resistance information will be analyzed for subjects receiving study drug who do not achieve SVR₁₂ and who have a post-baseline sample with HCV RNA ≥ 1000 IU/mL: 1) the amino acid variants in available post-baseline samples identified by NGS and comparison to the baseline sequence, 2) the amino acid variants in available post-baseline samples at signature resistance associated positions identified by NGS and comparison to the appropriate prototypic reference sequence, and 3) the persistence of viral resistance by NGS.

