6.3 Missing Data Imputation

Missing Data Imputation for SVR

HCV RNA values will be selected for analysis based on the analysis windows defined in Section 6.2.

For analyses of SVR, subjects' missing visit values will have backward imputation applied, if possible. For backward imputation, if the nearest HCV RNA value after the SVR window is unquantifiable or undetectable, then it will be used to impute the HCV RNA value in the SVR window. If a subject is missing an HCV RNA value within the appropriate SVR window after performing backward imputation, then this value will be imputed with an HCV RNA value from a local laboratory if present; otherwise, the HCV RNA value will be missing. Subjects with missing HCV RNA data in the analysis window, after imputations, will be imputed as a failure.

Regardless of the imputation method described above, if a subject starts another treatment for HCV, then all HCV RNA values for this subject measured on or after the start date of the new HCV treatment will be excluded from analyses. The subject will be considered a failure for summaries of viral response at all time points after the start of the new HCV treatment.

Missing Data Imputation for Virologic Failure

If HCV RNA values from the central laboratory are missing but a local laboratory value is present in the appropriate time period, then the local laboratory value will be used to assess post-treatment relapse and on-treatment virologic failure.

Missing Data Imputation for PRO Questionnaires

The handling of missing data for PROs will be as follows. If a respondent answers at least 50% of the items in a multi-item scale of the Short Form 36 Version 2 (SF-36v2) Health Status Survey, the missing items will be imputed with the average score of the answered items in the same scale. In cases where the respondent did not answer at least

50% of the items, the score for that domain will be considered missing. The Mental and Physical Component Summary measures will not be computed if any domain is missing. Missing data handling conventions for scores related to the Work Productivity and Activity Impairment Questionnaire (WPAI) – Hepatitis C are specified in Section 10.9.

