 - Employment status for a subject will be considered "missing" at a given visit if Q1 = missing and no positive hours recorded under Q2 and Q4.
- If a subject is "unemployed" or employment status is "missing," then S1, S2, and S3 will be set to "missing."
- If Q2 = 0 and Q4 = 0 or missing then Q2/(Q2 + Q4) = missing (i.e., S1 = missing).
- If Q2 = 0 and Q4 = 0, then set S3 to missing.
- If Q2 is missing or Q4 is missing, then set S1 and S3 to missing.
- If Q4 = missing, then DO NOT set Q5 = missing.
- If Q5 is missing, then apply the following rules:
 - If Q2 > 0, Q4 = 0, and Q5 = missing, then S3 = 100%.
 - If Q2 = 0, Q4 > 0, and Q5 = missing, then S3 is missing.
 - If Q2 > 0, Q4 > 0, and Q5 = missing, then S3 is missing.

Summary statistics for each protocol-specified visit (number of non-missing observations and mean) and for change from baseline to each protocol-specified visit (number of non-missing observations, mean, standard deviation, minimum and maximum) will be provided for (1) the SF-36v2 PCS score, MCS score, and 8 individual domain scores, and (2) the WPAI-HCV activity impairment, overall work impairment, absenteeism, and presenteeism scores.

The following analyses of PROs also will be performed:

- Number and percentage of subjects who have experienced an increase from baseline at each applicable time point of greater than or equal to 2.5 points in the SF-36 MCS and PCS;
- Number and percentage of subjects who have experienced an increase from baseline at each applicable time point of greater than or equal to 5 points in the SF-36 domain scores;

If a subject starts another treatment for HCV, then all PRO values for this subject measured on or after the start date of the new HCV treatment will be excluded from analyses.

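### SAP 10.8 admits the 24-week resistance sample with no condition on intervening HCV therapy, so variants selected or maintained by another regimen could be listed as GLE/PIB treatment-emergent or read as persistent (minor)

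*SAP*

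**What the plan says.** SAP 10.8 sets two time points for subjects who do not achieve SVR12. Time point 1 is "the sample closest in time after HCV virologic failure/treatment discontinuation with an HCV RNA level of" at least 1000 IU/mL. Time point 2 is "24 weeks post-DAA treatment, provided that resistance-associated variants were detected by NGS" at failure or discontinuation. Time point 2 has no HCV RNA threshold and no condition on other HCV therapy.

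A substitution is treatment-emergent under SAP 10.8 if it was below 2% at baseline and reaches 2% in a post-baseline sample, or if it is an enriched variant (a rise of at least 20 percentage points from baseline). Analysis 4 lists all such substitutions by subject and time point.

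Elsewhere the SAP cuts data off at re-treatment. Section 6.3 states that "all HCV RNA values for this subject measured on or after the start date of the new HCV treatment will be excluded from analyses", and adds: "The subject will be considered a failure for summaries of viral response at all time points after the start of the new HCV treatment". Section 10.9 states that "all PRO values for this subject measured on or after the start date of the new HCV treatment will be excluded from analyses".

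Protocol 5.3.3.3 names "3) the persistence of viral resistance by NGS" as a resistance output, and Protocol 4.2 makes emergence and persistence of variants an additional objective. Protocol 5.4.1 foresees that other anti-HCV therapy may start after discontinuation. Protocol 5.4.1.1 keeps virologic failures in follow-up for variants to 24 weeks post-treatment. SAP 7.3 defines post-treatment HCV medications from a dedicated eCRF entry.

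**The concern.** In two places the SAP recognises that data collected after a new HCV treatment no longer describe GLE/PIB. Section 10.8 has no matching rule for sequences, and SAP 12.1 gives no reason for the difference. The comparison is always with the sample taken before GLE/PIB, so the definition cannot separate a change selected by GLE/PIB from one selected by a later regimen acting on the same targets. A variant found at failure and then maintained by such a regimen could likewise be read as persisting after GLE/PIB.

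Time point 2 is the only later sample that 10.8 specifies and that can show persistence. At stake is the attribution of individual variants in a small set of listings.

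**Working it through.** **Rules side by side**

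| Data | Rule once a new HCV treatment starts | Source |
|---|---|---|
| HCV RNA | Excluded from the start date; subject counted as a failure from then on | SAP 6.3 |
| PRO | Excluded from the start date | SAP 10.9 |
| Sequences chosen by HCV RNA ≥ 1000 IU/mL (time point 1 and the sequencing triggers) | None stated; possibly covered through 6.3 | SAP 10.8 |
| Sequence at 24 weeks post-DAA (time point 2) | None stated; no HCV RNA criterion through which 6.3 could act | SAP 10.8 |

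Protocol 5.3.3.3 and 8.1.4 add no rule for sequences either.

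**Tracing one subject (illustrative; the documents give no re-treatment regimen, duration or rate).** Suppose relapse is seen at Day 28 after the last dose and variants are detected in that sample. Another 12-week regimen starts on Day 60 and ends on Day 60 + 84 = Day 144. The Week 24 sample falls on Day 168, the nominal day in SAP Table 2. It meets the only stated condition for time point 2. If virus is still sequenceable, any NS3 or NS5A substitution absent before GLE/PIB and now at 2% or more is treatment-emergent by definition and enters Analysis 4. A sequence exists only if the second regimen has not cleared the virus.

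**Scale.** The plan gives no figure on this point. Its 97% SVR12 assumption (Protocol 8.2, SAP 4.3) serves for scale. The protocol's half-widths reproduce from it:

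- GT5: 1.96 × √(0.97 × 0.03 / 30) = 0.061
- GT6: 1.96 × √(0.97 × 0.03 / 50) = 0.047

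Expected SVR12 non-responders = 80 × (1 − SVR12 rate):

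- at 99%: 0.8
- at 97%: 2.4
- at 95%: 4.0

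Let f be the share of non-responders who meet every condition: other HCV therapy before the Week 24 sample, sequenceable virus, and variants at failure or discontinuation. The documents do not give f; 0.10 to 0.50 is an assumption. At 97%:

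- expected affected subjects = 2.4 × f: 0.24 (f = 0.10) to 1.2 (f = 0.50)
- chance of at least one = 1 − (1 − 0.03 × f)^80: 21% (f = 0.10) to 70% (f = 0.50)

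The true f may be lower. Protocol 5.6.1 reports 8-week SVR12 of 33/34, 53/54 and 28/29 in GT1, GT2 and GT3, with no virologic failures to date. That is 3 non-responders among 117 (34 + 54 + 29), none of them a virologic failure. Those are other genotypes, but they show that an SVR12 rate near 97% need not produce sequenced failures.

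**The case against.** **Section 6.3 may already cover this.** If its exclusion of HCV RNA values applies to every analysis, a post-re-treatment sample could not be chosen by the 1000 IU/mL criterion. This is a fair reading for time point 1 and the sequencing triggers, so a reader who inferred that no resistance sample has any cut-off would go too far. But the sentence stands under the SVR imputation heading and names HCV RNA, not sequences, and 10.9 had to restate the rule for PROs. Its reach is unclear, and time point 2 lies outside it on either reading.

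**The harm needs a chain of events.** The subject must be a non-responder, have variants at failure or discontinuation, start another regimen before the sample, still have sequenceable virus, and carry a substitution attributable to that regimen. Protocol 5.6.3 expects no cross-resistance between IFN, RBV or SOF and either study drug, so the concern is mainly with regimens acting on NS3 or NS5A. This stands and limits the size.

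**The listings can be read by eye.** Analysis 4 is by time point, so a substitution first seen at Week 24 is visible as such, and post-treatment HCV medications are summarized separately. SAP 10.8 also has no category called persistent. This helps, but the listing would still carry the treatment-emergent label, and the reader would have to link two outputs to see why it may not apply.

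**Dropping the sequences loses information.** A Week 24 sequence after re-treatment may still show that a variant from the GLE/PIB period is detectable. This is a good reason to list such sequences separately rather than discard them.

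**Conclusion.** The point holds for time point 2 of SAP 10.8. The stated inclusion rule and the stated definition together could attribute another regimen's variants to GLE/PIB, and the SAP's own handling of HCV RNA and PRO data shows the remedy. For samples chosen by HCV RNA the position is unclear rather than wrong.

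The size is small. About 2.4 of 80 subjects are expected to be SVR12 non-responders at 97%, fewer will be sequenced virologic failures, and the 21% to 70% chance of at least one affected subject rests wholly on the assumed f. Only descriptive listings for an additional objective are affected. SVR12, on-treatment failure and relapse do not depend on these listings, and the Fisher's exact tests use baseline polymorphisms.

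Two stronger inferences are not supported:

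- **A large share of the resistance data.** A reader might divide one re-treated subject by 2.4 and infer that about 40% of the failure resistance data would be contaminated. But SVR12 non-responders include missing data imputed as failure (SAP 6.3) and premature discontinuations (SAP 10.1), which may yield no sequence. A re-treated subject may also still contribute a time point 1 sequence taken before the new therapy.
- **Very late samples.** A reader might infer from the Day 127 to 999 window that late samples would routinely enter. SAP Table 2 takes the result closest to Day 168, and follow-up ends at 24 weeks (Protocol 5.1.3), so the tail matters only for a late visit.

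Priority: minor.

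**What to change.** Add to SAP 10.8: sequences from samples collected on or after the start date of a new HCV treatment are not counted as GLE/PIB treatment-emergent, or as evidence of persistence, in Analysis 4. They are listed separately and flagged with the new-treatment start date from the post-treatment HCV medications eCRF. Applying this to every sequencing time point also settles how far 6.3 reaches.

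The cost is one sentence and one date condition in the programming, using post-treatment HCV medication data that the eCRF already captures. The downside is slightly fewer evaluable Week 24 sequences. The information is not lost, because the flagged listing keeps it.

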10.9 Patient Reported Outcomes

The following instruments will be used to collect PROs: Short Form 36 - Version 2 (SF-36v2), Work Productivity and Activity Impairment-Hepatitis C (WPAI-HCV) Specific Instrument Version 2.

The SF-36v2 measures dimensions of a patient's functional health and well-being in 8 domains and also provides 2 summary scores that characterize a patient's mental

(Mental Component Summary; MCS) and physical (Physical Component Summary; PCS) health status. Imputation will be applied to each domain as described in Section 6.3. The score for each of the 8 domains ranges from 0 to 100 and will be normalized according to the user manual.³ The standardization of the normalized scores will provide the norm-based scores with a mean of 50 and a standard deviation of 10. The two summary scores are based on the norm-based scores. Per the SF-36v2 instrument manual, the score for any item with multiple responses will be set to "missing." Subjects' responses to the SF-36v2 will be summarized for the PCS and MCS measures and 8 individual domain measures.

The WPAI Hepatitis C consists of 6 questions: Q1 = currently employed; Q2 = hours missed due to HCV-related health problems; Q3 = hours missed other reasons; Q4 = hours actually worked; Q5 = degree hepatitis C affected productivity while working (using a 0 to 10 VAS); Q6 = degree hepatitis C affected productivity in regular unpaid activities (VAS).

The four main impairment scores (S1 – S4) are expressed as percent impairment based on the above questions:

S1. Absenteeism (percent work time missed due to hepatitis C):

$$100 \times \left[\frac{Q2}{Q2 + Q4} \right]$$

S2. Presenteeism (percent impairment while working due to hepatitis C):

$$100 \times \left[\frac{Q5}{10} \right]$$

S3. Percent overall work impairment due to hepatitis C:

$$100 \times \left[\frac{Q2}{Q2 + Q4} + \left\{ 1 - \frac{Q2}{Q2 + Q4} \right\} \times \frac{Q5}{10} \right]$$

S4. Percent activity impairment due to hepatitis C:

$$100 \times \left[\frac{Q6}{10} \right]$$

The following missing data handling conventions are applied:

- Define Employment as a binary YES or NO variable where YES corresponds to "Employed" and NO corresponds to "Not Employed."
 - A subject will be considered "employed" at a given visit if Q1 = YES or Q2 > 0 or Q4 > 0.
 - A subject will be considered "unemployed" at a given visit if Q1 = NO and no positive hours recorded under Q2 and Q4 (i.e., if Q1 = NO AND Q2 ≤ 0 AND Q4 ≤ 0, then UNEMPLOYED).
 - Employment status for a subject will be considered "missing" at a given visit if Q1 = missing and no positive hours recorded under Q2 and Q4.
- If a subject is "unemployed" or employment status is "missing," then S1, S2, and S3 will be set to "missing."
- If Q2 = 0 and Q4 = 0 or missing then Q2/(Q2 + Q4) = missing (i.e., S1 = missing).
- If Q2 = 0 and Q4 = 0, then set S3 to missing.
- If Q2 is missing or Q4 is missing, then set S1 and S3 to missing.
- If Q4 = missing, then DO NOT set Q5 = missing.
- If Q5 is missing, then apply the following rules:
 - If Q2 > 0, Q4 = 0, and Q5 = missing, then S3 = 100%.
 - If Q2 = 0, Q4 > 0, and Q5 = missing, then S3 is missing.
 - If Q2 > 0, Q4 > 0, and Q5 = missing, then S3 is missing.

Summary statistics for each protocol-specified visit (number of non-missing observations and mean) and for change from baseline to each protocol-specified visit (number of non-missing observations, mean, standard deviation, minimum and maximum) will be provided for (1) the SF-36v2 PCS score, MCS score, and 8 individual domain scores, and (2) the WPAI-HCV activity impairment, overall work impairment, absenteeism, and presenteeism scores.

The following analyses of PROs also will be performed:

- Number and percentage of subjects who have experienced an increase from baseline at each applicable time point of greater than or equal to 2.5 points in the SF-36 MCS and PCS;
- Number and percentage of subjects who have experienced an increase from baseline at each applicable time point of greater than or equal to 5 points in the SF-36 domain scores;

If a subject starts another treatment for HCV, then all PRO values for this subject measured on or after the start date of the new HCV treatment will be excluded from analyses.

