8.1.3 Patient Reported Outcomes

The handling of missing data for patient reported outcomes (PROs) will be as follows. If a respondent answers at least 50% of the items in a multi-item scale of the SF-36v2, the missing items will be imputed with the average score of the answered items in the same scale. In cases where the respondent did not answer at least 50% of the items, the score for that domain will be considered missing. The Mental and Physical Component Summary measures will not be computed if any domain is missing. For WPAI Hepatitis C scores, no imputation will be performed for missing items.

The mean change from baseline to each applicable post-baseline timepoint in the SF-36v2 Mental Component Summary (MCS) and Physical Component Summary (PCS) scores; WPAI activity impairment due to hepatitis C, overall work impairment, absenteeism, and presenteeism scores will be summarized descriptively at each visit and for change from baseline to each visit. For each of these scores, mean change from Baseline to Final Treatment Visit and from Baseline to Post-Treatment Week 12 will be summarized using an analysis of covariance (ANCOVA) model with baseline score as a covariate.

The following analyses of patient reported outcomes (PROs) also will be performed:

- Cumulative number and percentage of subjects who have ever experienced an increase from baseline up through each applicable timepoint of greater than or equal to 3 points in the SF-36 MCS and PCS;
- Cumulative number and percentage of subjects who have ever experienced an increase from baseline up through each applicable timepoint of greater than or equal to 5 points in the SF-36 MCS and PCS;
- Cumulative number and percentage of subjects who have ever experienced an increase from baseline up through each applicable timepoint of greater than or equal to 5 points in the SF-36 domain scores;

Additional analyses of PROs will be performed as useful and appropriate.

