12.0 Summary of Changes

12.1 Summary of Changes Between the Latest Version of the Protocol and SAP Version 1.0

1. New expected confidence intervals are calculated in Section 4.3 Sample Size because the rule of choosing between the normal approximation method and

Wilson's score method for the primary endpoint has been updated in the protocol (also see Section 10.3)

2. All safety analyses have been changed to be performed only for the overall population because integrated safety analyses on Phase 3 studies showed no difference in safety profiles between subjects with compensated cirrhosis and without cirrhosis.
3. The race category of Black/non-Black has been changed to Asian/non-Asian in Section 7.1 and Section 10.6 because the Asian population is of interest to this study while very few Black subjects are expected to enroll. Also, different Asian types will be summarized among the baseline characteristics (Section 7.1).
4. The category of baseline HCV RNA level has been changed from 6,000,000 IU/mL to 2,000,000 IU/mL because it is a better cutoff based on previous studies.
5. Efficacy endpoints will also be summarized for the overall population (Section 10.6, Section 10.7 and Section 10.9) in order to provide results across all subjects in the study.
6. The integrated efficacy analysis combining GT5 and GT6 subjects from Studies M14-868 Part 4, M14-172 and M16-126 using meta-analytic methods has been removed because there is no plan for a label update with such data.
7. The resistance analyses (Section 10.8) have been updated to reflect current HCV project standards.
8. Text in PRO analyses of mean change from baseline has been updated for better clarity (Section 10.9).
9. Missing data handling conventions for scores related to the Work Productivity and Activity Impairment Questionnaire (WPAI) – Hepatitis C are specified in Section 10.9.
10. Methods for the assessment of hepatic laboratory values and hepatic laboratory abnormalities of interest have been added to Section 11.3.2 to reflect current HCV project standards.

11. The summaries of changes from baseline for vital signs have been replaced with summaries of visit values to reflect current HCV project standards (Section 11.4.2).

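### SAP 10.9 replaces the protocol's SF-36 responder definitions and omits the ANCOVA, and SAP 12.1 does not log the responder changes and describes the mean-change edit only as clarity

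*SAP*

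**What the plan says.** Protocol 8.1.3 (Patient Reported Outcomes) names two kinds of PRO analysis beyond visit-wise descriptive statistics.

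- **Responder counts.** The counting rule is "Cumulative number and percentage of subjects who have ever experienced an increase from baseline". It is applied to MCS and PCS at two cuts, "increase from baseline up through each applicable timepoint of greater than or equal to 3 points in the SF-36 MCS and PCS" and "increase from baseline up through each applicable timepoint of greater than or equal to 5 points in the SF-36 MCS and PCS", and to the domain scores at 5 points.
- **Mean change.** Change to the Final Treatment Visit and to Post-Treatment Week 12, for MCS, PCS and the four WPAI scores, "will be summarized using an analysis of covariance (ANCOVA) model with baseline score as a covariate".

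SAP 10.9 counts subjects at each time point with a gain of "greater than or equal to 2.5 points in the SF-36 MCS and PCS", and at each time point with at least 5 points in the domains. Its mean-change analysis is descriptive only, and no ANCOVA appears.

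SAP 12.1 is headed as the summary of changes between the latest protocol and SAP Version 1.0. Three of its items cite Section 10.9: item 5 (summaries for the overall population), item 9 (WPAI missing data) and item 8, which reads "Text in PRO analyses of mean change from baseline has been updated for better clarity (Section 10.9").

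**The concern.** The two documents define different responder analyses for the same instrument. Both protocol MCS/PCS cuts are gone, a cut found nowhere in the protocol takes their place, and cumulative counting has become visit-by-visit counting. The protocol allows additional PRO analyses, but that does not cover replacing the ones it names.

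The change log gives reasons for comparable edits: the race grouping (item 3), the baseline HCV RNA cutoff (item 4) and the vital-sign summaries (item 11). Someone relying on it would conclude that the responder analyses were unchanged. At stake is whether the SF-36 responder percentages can be traced to the protocol. This matters more than usual for self-reported improvement in an open-label, non-randomised study, where the percentage depends directly on the threshold chosen.

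**Working it through.** **1. Side by side**

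| Element | Protocol 8.1.3 | SAP 10.9 | Named in SAP 12.1? |
|---|---|---|---|
| MCS/PCS, lower cut | ≥3, ever | ≥2.5, per visit | No |
| MCS/PCS, higher cut | ≥5, ever | absent | No |
| Domain scores | ≥5, ever | ≥5, per visit | No |
| Mean change | descriptive and ANCOVA | descriptive only | Item 8, as clarity |

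The documents state no expected responder rate, so there is no figure to reproduce. The rest only gauges size.

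**2. Inputs**

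- From the documents: PROs are collected at Day 1, end of treatment and Post-Treatment Week 12 (protocol Appendices C and D; SAP 6.2, notes to Tables 1 and 3). There are thus two post-baseline visits. Scores are norm-based with SD 10 (SAP 10.9), which is not the SD of change.
- Assumed: normal change with the same mean μ (1 to 3) and SD σ (6 to 10) at both visits, correlation ρ between the two changes of 0.3 to 0.8, no missing data.

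**3. Formulas.** With z = (c − μ)/σ for cut c:

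- per visit: P = 1 − Φ(z)
- ever over two visits: P = 1 − Φ₂(z, z; ρ), where Φ₂ is the bivariate normal distribution function

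At end of treatment, the first post-baseline PRO visit, ever and per-visit coincide. They can differ only at Post-Treatment Week 12.

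**4. One case: μ = 2, σ = 8, ρ = 0.5**

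- Per visit: ≥2.5, z = 0.0625, 47.5%; ≥3, z = 0.125, 45.0%; ≥5, z = 0.375, 35.4%.
- Ever: ≥3, 61.5%; ≥5, 50.8%.
- End of treatment: 47.5 − 45.0 = 2.5 points above the protocol's 3-point rate.
- Post-Treatment Week 12: 61.5 − 47.5 = 14.0 points below ever-3.
- A 5-point cut with the same inputs, as for the domains: 50.8 − 35.4 = 15.4 points lower per visit than ever.

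**5. Range** over μ = 1, 2, 3, σ = 6, 8, 10 and ρ = 0.3 to 0.8

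- End of treatment: ≥2.5 exceeds ≥3 by 2.0 to 3.3 points. Among 80 subjects that is 0.020 × 80 = 1.6 to 0.033 × 80 = 2.6 people.
- Post-Treatment Week 12: per-visit ≥2.5 is below ever ≥3 by 6.5 points (μ = 1, σ = 6, ρ = 0.8) to 18.2 points (μ = 3, σ = 10, ρ = 0.3), roughly 7 to 18. Fixing ρ at 0.6 would give only 10.7 to 12.8, so the width comes mainly from the correlation.

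At the same visit, the ≥2.5 count can never be smaller than the ≥3 count. At Post-Treatment Week 12 the two definitions are not nested: someone at +4 then +1 is a responder only under the protocol, and someone at +1 then +2.7 only under the SAP. The direction there rests on the assumptions.

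**6. ANCOVA.** The protocol names baseline as covariate and no group factor. Fit change = a + b(baseline − mean baseline) + error by least squares to one group. Because the centred covariate sums to zero, the estimate of a is the raw mean change. Only the standard error differs.

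**The case against.** The strongest reply is that these are supportive descriptive tables. PROs are absent from the primary and secondary objectives, no hypothesis is tested, and the SAP exists to elaborate the protocol's methods. It keeps the 5-point domain cut and adds mean-change summaries for all eight domains. At end of treatment the new cut moves about 2 subjects in 80, against a 95% half-width of 1.96 × √(0.475 × 0.525/80) ≈ 11 points. All of this stands and limits the importance of the point. The half-width comparison is less telling than it looks, because the two definitions are applied to the same subjects and the gap between them is not sampling error.

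A reader might also infer stronger things that the documents do not support:

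- *That the SAP lowers the bar and so inflates response.* The lower cut raises the rate, but per-visit counting lowers it. Under the assumptions used, the net effect against ever-3 at Post-Treatment Week 12 is downward.
- *That 12.1 presents the responder change as clarity.* Item 8 covers only mean-change text. The responder changes are omitted, not mislabelled.
- *That the cut was chosen after seeing data.* Nothing in either document shows this.
- *That the responder percentage will be the headline PRO result.* Neither document ranks the PRO summaries.
- *That dropping the ANCOVA loses an estimate.* As specified, it leaves the mean change unchanged.

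**Conclusion.** The point holds as a discrepancy between protocol and SAP that the change log does not disclose. That conclusion rests on the text alone.

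The sizes, about 2 to 3 points higher at end of treatment and roughly 7 to 18 points lower than ever-3 at Post-Treatment Week 12, rest wholly on assumed normal changes and an assumed correlation, and should be read as illustration. Because the two changes pull in opposite directions, the protocol-defined rate cannot be recovered from the SAP's table.

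SVR12, virologic failure, relapse and safety are untouched. This should be corrected, but it does not threaten the trial's conclusions.

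**What to change.** - **SAP 10.9:** add back the cumulative ever-3 and ever-5 rows for MCS and PCS and the cumulative ever-5 row for the domain scores. Keep the per-visit 2.5-point table as an additional summary.
- **SAP 12.1:** list the new 2.5-point cut, the change from ever to per-visit counting (including the domains) and the ANCOVA removal, each with its reason. Item 8 should say that a model was dropped.
- **ANCOVA:** restoring it is optional, since it would alter only the standard error. If it stays out, the log entry is enough.

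The cost is SAP wording and a few descriptive rows from data already collected. No protocol amendment is needed, because the change brings the SAP back to the protocol.
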